4.2.2.5.2 Safety Analysis Set

The summaries described in the above section 4.2.2.5.1 will be produced using the SAF for:

- savolitinib (300 mg od and 600 mg od, respectively) in combination with osimertinib in patients with EGFRm+, MET amplified/overexpressed (FISH10+ and/or IHC90+), locally advanced or metastatic NSCLC who have progressed following treatment with 1L osimertinib
- savolitinib (300 mg od, 300 mg bid and 600 mg od, respectively) in combination with osimertinib in patients with EGFRm+, MET amplified/overexpressed (FISH5+ and/or IHC50+), locally advanced or metastatic NSCLC who have progressed following osimertinib

4.2.2.6 Secondary Endpoint – EORTC QLQ-C30 and QLQ-LC13

4.2.2.6.1 Target Population Analysis Set

For EORTC QLC-C30 and QLQ-LC13, respectively, the observed values and change from baseline of functional/symptom scales, the individual items and the global health status scores will be summarised over time using descriptive statistics.

The improvement rate, i.e. proportion of patients with improvements, and 95% Clopper-Pearson CIs for each scale/item score will be summarised. The improvement rate is based on the number of patients who have a baseline individual score ≥ 10 .

Time to deterioration for the symptom scales and the individual items will be summarised using Kaplan-Meier methodology. Median and quartile time to deterioration and the percentage of patients being free of deterioration at selected timepoints, along with the 95% CI, will be presented. The population for analysis of time to symptom deterioration will include a subset of the Safety analysis set who have EORTC QLQ-LC13 or EORTC QLQ-C30 baseline scores ≤ 90 .

The compliance and evaluable rate (%) will be presented together with the number of evaluable, received and expected questionnaires at each timepoint.

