- Dyspnoea (multi-item scale based on three questions: “Were you short of breath when you rested; walked; climbed stairs”) (LC13),
- Cough: one item (“How much did you cough?”) (LC13),
- Pain: one item (“Have you had pain in your chest”) (LC13).
- Fatigue (a composite score of three items: “Did you need rest; Have you felt weak; Were you tired”) (C30)
- Appetite loss: one individual item (“Have you lacked appetite”) (C30)

Definition of clinically meaningful changes

Changes in score compared to baseline will be evaluated. A minimum clinically meaningful change is defined as a change in the score from baseline of ≥ 10 for scales/items from the QLQ-LC13 and the QLQ-C30 ([Osoba et al 1998](#)).

For example, a clinically meaningful deterioration or worsening in chest pain (as assessed by QLQ-LC13) is defined as an increase in the score from baseline of ≥ 10 . A clinically meaningful improvement in fatigue (as assessed by QLQ-C30) is defined as a decrease in the score from baseline of ≥ 10 .

At each post-baseline assessment, change in symptoms/functioning from baseline will be categorised as improved, stable or worsening as shown in [Table 14](#).

Table 14 Visit Response for HRQoL and disease-related symptoms

Score	Change from baseline	Visit Response
QLQ-LC13/QLQ-C30 symptom scales/items	≥+10	Worsened
	≤-10	Improved
	Otherwise	Stable
QLQ-C30 functional scales and Global health status/QoL	≥+10	Improved
	≤-10	Worsened
	Otherwise	Stable

Time to symptom deterioration

Time to deterioration in symptoms, functioning and global health status/QoL will be evaluated, more details will be specified in the SAP.

Symptom improvement rate

Improvement in symptoms, functioning and global health status/QoL will be evaluated, more details will be specified in the SAP.

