Higher scores on the global health status and functioning scales indicate better health status/function. Higher scores on the symptom scales indicate greater symptom burden. For each subscale, if less than 50% of the subscale items are missing, then the subscale will be divided by the number of non-missing items and multiplied by the total number of items on that subscale. If at least 50% of the items are missing, then that subscale will be treated as missing. Missing single items are treated as missing. The reason for missing questionnaires will be identified and recorded. If there is evidence that the missing data are systematic, missing values will be handled to ensure that any possible bias is minimised.

The primary PRO outcome measures will be 5 patient-reported lung cancer symptoms, namely:

- Dyspnoea (multi-item scale based on three questions: “Were you short of breath when you rested; walked; climbed stairs”) (LC13),
- Cough: one item (“How much did you cough?”) (LC13),
- Pain: one item (“Have you had pain in your chest”) (LC13).
- Fatigue (a composite score of three items: “Did you need rest; Have you felt weak; Were you tired”) (C30)
- Appetite loss: one individual item (“Have you lacked appetite”) (C30)

Changes in score compared to baseline will be evaluated. A minimum clinically meaningful change is defined as a change in the score from baseline of ≥ 10 for scales/items from the QLQ-LC13 and the QLQ-C30.

At each post-baseline assessment, change in symptoms/functioning/items from baseline will be categorised as improved, stable, or worsening as shown in Table 10.

Table 10 Visit response for QLQ-C30/QLQ-LC13 subscales

Score	Change from baseline	Visit Response
QLQ-LC13/QLQ-C30 symptom scales/items	$\geq+10$	Worsened
	≤-10	Improved
	Otherwise	Stable
QLQ-C30 functional scales and Global health status/QoL	$\geq+10$	Improved
	≤-10	Worsened
	Otherwise	Stable

Time to symptom deterioration

For each of the symptoms scales/items in EORTC QLQ-C30 and QLQ-LC13, time to symptom deterioration will be defined as the time from first dose of study treatment until the date of first clinically meaningful symptom deterioration (an increase in the score from baseline of ≥ 10) or death (by any cause) in the absence of a clinically meaningful symptom deterioration, regardless of whether the patient withdraws from study treatment or receives another anti-cancer therapy prior to symptom deterioration.

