Death will be included as an event only if the death occurs within two visits of the last PRO assessment where the symptom change could be evaluated. Patients whose symptoms (as measured by EORTC QLQ-C30 and QLQ-LC13) have not shown a clinically meaningful deterioration and who are alive at the time of the analysis will be censored at the time of their last PRO assessment where the symptom could be evaluated. Also, if symptoms progress after two or more missed PRO assessment visits or the patient dies after two or more missed PRO assessment visits, the patient will be censored at the time of the last PRO assessment where the symptom could be evaluated. If a patient has no evaluable visits or does not have baseline data, they will be censored at Day 1. The population for analysis of time to symptom deterioration will include a subset of the Safety analysis set who have EORTC QLQ-LC13 or EORTC QLQ-C30 baseline scores ≤ 90 .

Symptom improvement rate

The symptom improvement rate will be defined as the number (%) of patients with two consecutive assessments which showed a clinically meaningful improvement (a decrease from baseline score ≥ 10 for EORTC QLQ-LC13 scales/items and EORTC QLQ-C30 scales/items) in that symptom from baseline. The denominator will consist of a subset of the Safety analysis set who have a baseline symptom score ≥ 10 .

Compliance rate

The compliance rate (%) and the evaluability rate (%) for EORTC QLQ-C30 and QLQ-LC13 will be calculated. This is based on:

- Received questionnaire = a questionnaire that has been received and has a completion date and at least one individual item completed.
- Expected questionnaire = a questionnaire that is expected to be completed at a scheduled assessment time, i.e. a questionnaire from a patient who has not withdrawn from the study at the scheduled assessment time.
- Evaluable questionnaire = a questionnaire with a completion date and at least one subscale that is non-missing.

The compliance rate is the number of evaluable questionnaires divided by the number of expected questionnaires, multiplied by 100. The evaluability rate is the number of evaluable questionnaires divided by the number of received questionnaires, multiplied by 100.

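### The QLQ improvement rate uses a baseline-of-at-least-10 denominator for every scale, which does not fit the functional scales and global health status, and improvement on those scales has no two-assessment definition

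*SAP*

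**What the plan says.** Protocol 9.4.3.3, under its sub-heading on the symptom improvement rate, states that "Improvement in symptoms, functioning and global health status/QoL will be evaluated" and leaves the details to the SAP.

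SAP 3.2.3.1.1 sets the direction of the scores: "Higher scores on the global health status and functioning scales indicate better health status/function", while higher symptom scores mean more burden. Its Table 10 (the same as protocol Table 14) follows this. On symptom scales and items, a change of -10 or less is Improved. On functional scales and global health status, +10 or more is Improved and -10 or less is Worsened.

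The same section then defines the symptom improvement rate. A patient counts if two consecutive assessments show "a decrease from baseline score" of at least 10 "for EORTC QLQ-LC13 scales/items and EORTC QLQ-C30 scales/items) in that symptom from baseline". On the denominator it says: "The denominator will consist of a subset of the Safety analysis set who have a baseline symptom score" of at least 10.

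SAP 4.2.2.6.1 says what will be reported. It first names the "change from baseline of functional/symptom scales, the individual items and the global health status scores". It then plans the proportion of patients with improvements, and says that "95% Clopper-Pearson CIs for each scale/item score will be summarised". It closes with one denominator for all of them: "The improvement rate is based on the number of patients who have a baseline individual score" of at least 10. The word *symptom*, present in the definition section, is gone.

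**The concern.** A baseline threshold in a responder rate should admit patients who have room to respond and leave out those who do not. A threshold of at least 10 does this where response is a fall of 10 points. Where response is a rise of 10 points, it admits patients at the ceiling and removes patients at the floor.

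The scope of the rate looks deliberate. The next paragraph of 4.2.2.6.1 limits time to deterioration to symptom scales and individual items, whereas the improvement rate carries no such limit. The programmer therefore has to produce a rate for functioning and global health. The stated denominator does not fit those scales, and the only two-assessment rule in the SAP was written for symptoms.

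At stake is how quality-of-life benefit is described in the study report. Rates with exact confidence intervals would rest on a set that includes patients who could not have improved, in a proportion that depends on the baseline mix of each regimen.

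**Working it through.** The plan states no figure that could be reproduced. The check compares the rules with each other, then sizes the denominator effect under stated assumptions.

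**Inputs.** The scoring formulas, score directions, Table 10 and the rate definition come from SAP 3.2.3.1.1. The scope and denominator of the reported rate come from SAP 4.2.2.6.1. The analysis sets come from SAP 4.2.2.6.1 and 4.2.2.6.2.

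**Step 1: room to respond on a 0 to 100 scale.**
- Response is a fall of at least 10: possible only if baseline - 10 >= 0, so baseline >= 10. The SAP threshold fits.
- Response is a rise of at least 10: possible only if baseline + 10 <= 100, so baseline <= 90. The SAP threshold does not fit.

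The SAP applies this logic elsewhere. Time to symptom deterioration, where the event is a rise of at least 10, is restricted to baseline scores of 90 or less.

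**Step 2: the rules side by side.** With items scored 1 to 4 (the SAP's own example, range 3), functional score = (1 - (RS - 1)/3) x 100 and symptom score = ((RS - 1)/3) x 100.

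| Scale | Raw score | Score | Change | Table 10 | Meets a decrease of at least 10? | Baseline at least 10? | Room to improve by 10? |
|---|---|---|---|---|---|---|---|
| Symptom | 2 to 1 | 33.3 to 0.0 | -33.3 | Improved | Yes | Yes | Yes |
| Functional | 2 to 1 | 66.7 to 100.0 | +33.3 | Improved | No | Yes | Yes |
| Functional | 1 to 2 | 100.0 to 66.7 | -33.3 | Worsened | Yes | Yes | No |
| Functional | 4 to 3 | 0.0 to 33.3 | +33.3 | Improved | No | No | Yes |

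The symptom row is consistent throughout. In the last two functional rows, the patient who cannot improve is in the denominator and the patient who does improve is out of it. Neither result depends on which numerator is used. Global health status is scored by the symptom-type formula, but higher is better, so step 1 applies to it as well.

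**Step 3: size of the denominator effect.** The documents give no baseline distribution. Assume 100 patients and 20 true improvers, none of them with a baseline below 10. Assume that 10% to 40% have a baseline above 90 and 0% to 5% a baseline below 10.

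- Denominator as written (baseline at least 10): 20/100 = 20.0% with none below 10, and 20/95 = 21.1% with 5% below 10.
- Denominator of baseline 90 or less: 20/90 = 22.2% with 10% above 90, 20/80 = 25.0% with 20%, and 20/60 = 33.3% with 40%.

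**Step 4: reach.** There are five functional scales and one global scale, so six scales. The rate is planned for the TPAS (1 set) and, in the SAF, for three regimens in two MET populations (3 x 2 = 6 sets). That gives 7 x 6 = up to 42 reported rates.

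**The case against.** The best reply is that the SAP already knows which way these scales run. The decrease rule sits under a symptom heading, refers to improvement in that symptom, and uses a baseline symptom score. Table 10, in the same section, gives the correct direction for functional and global scales. SAP 4.2.2.6.1 speaks only of patients with improvements and does not repeat the decrease rule.

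This answers a stronger charge that a reader might infer: that the plan counts worsening as improvement, so that a functional score going from 80 to 60 is a success and one going from 60 to 80 is not. The documents do not support that as the plan's rule. It follows only if the general mention of QLQ-C30 scales and items in 3.2.3.1.1 is joined to the all-scales scope of 4.2.2.6.1, the symptom wording is set aside, and Table 10 is contradicted. It is one literal reading.

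The reply does not rescue the rest. Table 10 classifies single visits and says nothing about who belongs in the denominator, and 4.2.2.6.1 states that denominator for every scale without exception. Nor does Table 10 say whether improvement on a functional scale needs two consecutive assessments. The SAP gives no such rule for scales on which the protocol wants improvement evaluated.

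Two further replies are fair. First, the impact is small. The listed secondary PRO endpoint is mean change from baseline, and the five primary PRO measures are all symptoms, for which the current rule is right. Second, a cut at 90 is a choice that the documents do not impose on functional scales, although it follows from the 10-point criterion and mirrors the SAP's own cut for time to deterioration.

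**Conclusion.** The point holds for the denominator and for the missing definition. As written, the improvement rates for the five functional scales and global health status include patients above 90 who cannot gain 10 points and exclude patients below 10 who can. The SAP gives those scales no two-assessment rule of their own. Borrowing the symptom rule would contradict Table 10, and using Table 10 leaves the two-assessment requirement open.

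The denominator conclusion needs only the 0 to 100 scoring, the 10-point criterion and the direction of the scales, all stated in the SAP. Its size is not known. The contrast of 20.0% to 21.1% with 22.2% to 33.3% rests wholly on the assumed baseline shares and number of improvers. Ceiling patients dilute a rate; they do not reverse it.

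The consequence is confined to descriptive secondary PRO rates. No test, error rate, primary result, mean-change endpoint or primary PRO symptom is affected. The correction is still worth making, because a stated rule gives an unsuitable denominator and costs little to repair.

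**What to change.** In SAP 3.2.3.1.1, add a sentence: for the QLQ-C30 functional scales and global health status, improvement is an increase from baseline of at least 10 at two consecutive assessments, in line with Table 10, among patients with a baseline score of 90 or less. In SAP 4.2.2.6.1, confine the baseline-of-at-least-10 denominator to symptom scales and items, and refer to the new denominator for the other six scales. The present decrease rule then stays as it is for symptoms.

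If functional and global rates are not wanted, limit the improvement rate in 4.2.2.6.1 to symptom scales and items. Record that departure from protocol 9.4.3.3 in SAP section 6, which does not mention it now.

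Either way the cost is about two sentences and the matching derivation for six scales. No new data are needed.

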4.2.2.6.2 Safety Analysis Set

The summaries described in the above section 4.2.2.6.1 will be produced using the SAF for:

- savolitinib (300 mg od, 300 mg bid and 600 mg od, respectively) in combination with osimertinib in patients with EGFRm+, MET amplified/overexpressed (FISH10+ and/or IHC90+), locally advanced or metastatic NSCLC who have progressed following osimertinib
- savolitinib (300 mg od, 300 mg bid and 600 mg od, respectively) in combination with osimertinib in patients with EGFRm+, MET amplified/overexpressed (FISH5+ and/or IHC50+), locally advanced or metastatic NSCLC who have progressed following osimertinib.

4.2.2.7 Secondary Endpoint – Pharmacokinetics

4.2.2.7.1 PK Analysis Set

PK analyses will be produced using the PK analysis set for:

- savolitinib (300 mg bid, 300 mg bid and 600 mg od, respectively) in combination with (FISH5+ and/or IHC50+), locally advanced or metastatic NSCLC who have progressed following osimertinib.

Plasma concentrations of osimertinib, savolitinib and their metabolites after single and multiple dosing will be summarised by nominal sample time and visit for All Patients in the PK analysis set and by savolitinib starting dose. Concentrations and PK parameters will be summarised using descriptive statistics (geometric mean [Geomean], geometric coefficient of variation [gCV%], geometric standard deviation [gSD], arithmetic mean, standard deviation [SD], median, minimum (min), maximum (max), and n) as applicable. For diagnostic parameters, Geomean, gCV% and gSD will not be reported.

Individual plasma concentration-time profiles may be presented. Plots will be produced by actual time, and on both linear scale and semi-logarithmic scale for the All Patients population and by savolitinib starting dose.

Plasma concentrations of savolitinib, osimertinib and their metabolites by nominal visit and timepoint may also be plotted using box plots on both linear scale and semi-logarithmic scale for the All Patients population.

Finally, geometric mean (\pm gSD) plasma concentrations of savolitinib, osimertinib and their metabolites by nominal timepoint may be plotted on both linear scale and semi-logarithmic scale for the All Patients population.

Concentrations below the lower limit of quantitation (BLQ) will be reported in the following way:

- Individual BLQ concentrations are reported as NQ (not quantifiable).
- For summary data:
 - a. If, at a given time point, 50% or less of the concentrations are not quantifiable [NQ], the geomean, gCV%, gSD, arithmetic mean and standard deviation [SD] are calculated by

substituting the LLOQ for values which are NQ.

- b. If more than 50%, but not all, of the concentrations are NQ, the geomean, gCV%, gSD, arithmetic mean and SD are reported as not calculable [NC]. The maximum value is reported from the individual data, and the minimum and median are set as NQ.
- c. If all the concentrations are NQ, the geomean and arithmetic mean are reported as NQ and the gCV%, gSD and SD as NC.
- d. The number of values below LLOQ are reported for each time point along with the total number of collected values.

Three values >LLOQ are required as a minimum for a concentration to be summarised. Two values are presented as a minimum and maximum with the other summary statistics as NC. The lower limit of quantitation will be reported in the CSR and in PK tables, figures and listings.

PK concentration data listings will be presented to the same number of significant figures as the data received from the bioanalytical laboratory (usually but not always to 3 significant figures) and against the same units as received.

PK concentration descriptive statistics will all be presented to 4 significant figures with the exception of the min and max which will be presented to 3 significant figures and n and n<LLOQ which will be presented as integers.

Further rules regarding PK parameters presentation can be found in Appendix “B”.

4.2.2.8 Secondary Endpoint – Biomarkers

4.2.2.8.1 Target Population Analysis Set

Biomarker endpoints will be analysed for TPAS.

ctDNA status will be presented including the number and percentage of patients with detectable EGFR mutations at baseline and available data at 6-weeks, split by ctDNA clearance and non-clearance.

The absolute change and the percentage change in EGFR mutation ctDNA allele frequencies at Week 6 will be summarised with descriptive statistics (n, mean, SD, median, min, max). Individual-level changes from baseline to all post-baseline timepoints will be summarised for all patients.

4.2.2.9 Exploratory Endpoint – CNS Metastases

4.2.2.9.1 Contribution of Components Analysis Set

The CNS metastases analyses will be produced using the CAS for:

- 300 mg bid (savolitinib) + osimertinib
- 300 mg bid (savolitinib) + placebo

The CNS PFS, CNS ORR and CNS DoR by BICR will be explored to assess the efficacy of savolitinib plus osimertinib and savolitinib plus placebo, respectively, on CNS metastases in patients with CNS metastases at baseline.

The presence/absence of CNS lesions at progression by BICR in patients without CNS metastases at baseline will be presented using descriptive statistics.

4.2.2.10 Exploratory Endpoint – PRO- CTCAE

Individual items will be summarised with the number and proportion of patients in each response category over time.

4.2.2.10.1 Safety Analysis Set

The analyses described in the above section 4.2.2.10 will be produced using the SAF for:

- savolitinib (300 mg od, 300 mg bid and 600 mg od, respectively) in combination with osimertinib in patients with EGFRm+, MET amplified/overexpressed (FISH10+ and/or IHC90+), locally advanced or metastatic NSCLC who have progressed following osimertinib
- savolitinib (300 mg bid, 300 mg bid and 600 mg od, respectively) in combination with osimertinib in patients with EGFRm+, MET amplified/overexpressed (FISH5+ and/or IHC50+), locally advanced or metastatic NSCLC who have progressed following osimertinib.

4.2.2.11 Exploratory Endpoint – PGIS

The question will be summarised with the number and proportion of patients in each of the six response categories over time. Also, the change from baseline in the severity of cancer symptoms will be presented as the proportion of patients with no change (e.g., mild to mild), 1 category improvement (e.g., mild to none), ≥ 2 category improvement (e.g., severe to mild), 1 category deterioration (e.g., none to mild), and ≥ 2 category deterioration (e.g., mild to severe) at each visit by group. The data will be analysed based

on the following re-grouped categories at baseline: None (no symptoms), Mild (very mild and mild), Moderate, and Severe (very severe and severe).

